## **Research Designing**

# Specific aim

To determine the efficacy of different warming method according to hypothermia risk estimation to prevent perioperative hypothermia and reduce perioperative complications.

[figure not shown]
#### Methods

# Overview of design

This is a randomized, single-blinded, multi-center study clinical trial to determine both clinical outcomes of stratified warm strategy to prevent intraoperative hypothermia. Patients enrolled into this trial will be from elective major surgery population in PUMC Hospital, Beijing Hospital and Xuanwu Hospital from April 1, 2019 to March 31, 2021. We plan to enroll approximately 800 patients. We review the medical records and have a face-to-face interview to determine whether the patient is eligible for the study according to the inclusion and exclusion criteria. Hypothermia risk will be estimated through PREDICTOR model in all eligible patients. According to hypothermia risk level, these patients will be stratefied into high, moderate and low risk group. Patients in each group will be randomly categorize into warm group and control group. For controll group traditional passive warm was used, which means cotton blanket was used to prevent hypothermia. While, for active warm group, different warm strategy are used according to risk level, prewarm for 30min only for low risk patients, prewarm 30 min and fluid warm for moderate risk patients, prewarm and forced-air warm throughout operation and fluid warm for high risk patients. Temperature will be record though the operation. All participants were followed up every day after surgery until 6 month after operations. Any post operation complication will be recorded carefully.

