#### Plans for randomization and blinding

Randomization: Patients will be randomized using stratified blocked randomization. The random treatment assignments are placed in sealed, numbered, and opaque envelops who will not be involved in opening them. Two staffs signed and recorded the next unopened envelope before opening the envelope. Investigators will access the allocation about an hour before surgery is expected to start, after consent is obtained. Allocation will thus be remained concealed until the last practical moment.

Blinding: Patients are all blind to the allocation.

Reduce confounding factor: Patients in GA group were given 1.5-2mg/kg Propofol, 0.8mg/kg rocuronium, 2ug/kg fentanyl for induction of anesthesia. After tracheal intubation, anesthesia was continued with sevoflurane in 50% nitrous oxide with oxygen, and end-tidal anesthesia gas is maintained 0.9-1.2 MAC. Supplemental fentanyl doses of 50ug are administered for blood pressure elevation or heart rate increases amounting to more than 10% of baseline.

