## Outcome variables

Primary outcome: hypothermia incidence during operation

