#### **Statistical issues**

## Analysis plan

Student's t test (for Intraoperative blood loss/blood transfusion, Length of stay in PACU) Wilcoxon rank-sum test (for Length of Stay in hospital, Length of Stay in ICU, MMSE, AVLT, Digital span, Color Word stroop, digit symbol substitution),

 $\chi^2$  test (for hypothermia incidence, Incidence of shiver, Surgical site infection: WIthin 30 days postoperative, Adverse cardiovascular events: Within 30 days postoperative, Incidence of postoperative cognitive disoerder at7day postoperative) will be used to compare the primary and secondary outcomes between groups.

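### No temperature is specified before prewarming, so the primary comparison, though unbiased, cannot separate prevention from rewarming and forgoes a likely prognostic covariate

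*Combined protocol and SAP*

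**What the plan says.** - **Measurement.** Overview of design: "Temperature will be record though the operation". No other section gives a time, site, device or interval for temperature.
- **Outcome.** Outcome variables: "Primary outcome: hypothermia incidence during operation". No threshold or duration is given, and no rule for a patient who is already cold on arrival.
- **Warm arm.** Overview of design: "prewarm for 30min only for low risk patients, prewarm 30 min and fluid warm for moderate risk patients". High-risk patients also receive prewarming, with forced-air and fluid warming. In the low-risk stratum prewarming is the whole intervention.
- **Control arm.** "For controll group traditional passive warm was used, which means cotton blanket was used to prevent hypothermia". No prewarming is described.
- **Timing of allocation.** Plans for randomization and blinding: "Investigators will access the allocation about an hour before surgery is expected to start, after consent is obtained".
- **Prognostic information before randomisation.** "Hypothermia risk will be estimated through PREDICTOR model", and the resulting risk level is the stratification factor. The model's inputs are not listed.
- **Analysis.** The Analysis plan assigns the primary outcome to an unadjusted chi-square "test (for hypothermia incidence, Incidence of shiver" and other binary outcomes). No covariate or stratum term is planned.

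**The concern.** The allocation is opened about an hour before surgery, and prewarming fits between that moment and the first specified temperature. In the control arm the first intraoperative reading follows no active warming. In the warm arm it follows treatment. The two readings are therefore not comparable as baselines, and adjusting for them would remove part of the treatment effect.

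Two things are at stake. First, the Overview of design describes the strategy as preventing hypothermia during surgery. A control patient who arrives cold may be recorded as hypothermic, while a similar warm-arm patient may be rewarmed before the first reading. Without a pre-treatment value, that difference looks the same as a prevented case. Second, a pre-treatment temperature is likely to predict the intraoperative nadir, and the planned test has nothing of the kind to adjust for. A reading not taken before prewarming cannot be recovered later.

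**Working it through.** **1. The plan's own figure.** The stated total is 793 (two-sided alpha 0.05, power 0.90, control incidence 39.9%, effect size 0.36 on an undefined scale, 10% dropout). Per arm,

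n = [1.96·√(2·p̄(1−p̄)) + 1.2816·√(p₁(1−p₁) + p₂(1−p₂))]² / (p₁−p₂)²

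- Reading 0.36 as a relative reduction: p₂ = 0.399 × 0.64 = 0.2554, n = 223, total 446, and 446/0.9 gives 496.
- p₂ = 0.284 (difference 11.5 points): n = 356, total 712, and 712/0.9 gives 792.

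The figure of 793 does not reproduce under any reading of 0.36 that was tried. It corresponds to about 28.4% in the warm arm. The present point does not depend on this mismatch, but it means the gain must be shown for more than one effect. Analysed patients: 793 × 0.9 / 2 = 356.85, so 356 per arm.

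**2. Share arriving cold (assumptions; the documents give no temperatures).** With a 36 °C limit and normal arrival temperature, the share is Φ((36 − mean)/SD):

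- mean 36.7, SD 0.30: 1.0%
- mean 36.6, SD 0.30: 2.3%
- mean 36.5, SD 0.35: 7.7%

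**3. What that share could do to interpretation.**

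- *Ceiling for rewarming.* Suppose every patient arriving cold counts as an event under control, and all are rewarmed and stay warm under treatment. The share then adds its full size to the risk difference. Against 11.5 points that is 1.0/11.5 = 9%, 2.3/11.5 = 20% or 7.7/11.5 = 67% of the effect.
- *Opposite case, dilution.* Suppose patients arriving cold are events in both arms and the 36% reduction applies only to new cases: p₂ = c + (0.399 − c) × 0.64, with 357 per arm.

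| Share c | p₂ | Overall reduction | Power |
|---|---|---|---|
| 0% | 25.5% | 36.0% | 98.4% |
| 1% | 25.9% | 35.1% | 98.0% |
| 2% | 26.3% | 34.2% | 97.3% |
| 5% | 27.3% | 31.5% | 94.6% |
| 10% | 29.1% | 27.0% | 85.8% |

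Without a baseline the trial cannot say where between these cases it lies.

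**4. Precision.** Model: latent nadir T = r·B + √(1−r²)·e + δ·G, with B (baseline) and e standard normal and G = 1 in the warm arm. An event is T < Φ⁻¹(0.399), and δ = Φ⁻¹(0.399) − Φ⁻¹(p₂). A logistic Wald test was run without and with B, 356 per arm, 5,000 replicates (standard error of each power at most √(0.25/5000) = 0.7 points).

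| Warm-arm rate | r = 0.3 | r = 0.5 | r = 0.6 |
|---|---|---|---|
| 32.4% (δ 0.20) | 0.548 → 0.580 | 0.548 → 0.625 | 0.547 → 0.660 |
| 28.4% (δ 0.31) | 0.898 → 0.915 | 0.894 → 0.937 | 0.906 → 0.959 |
| 25.5% (δ 0.40) | 0.984 → 0.987 | 0.983 → 0.994 | 0.985 → 0.997 |

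Gains in this run are 3 to 11, 2 to 5 and about 0 to 1 points. Shorter runs of the same model (1,000 to 1,500 replicates) gave gains up to about 13 points at 32.4% and 7 points at 28.4%. The risk stratum is not in the model.

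**The case against.** A reader might infer more than the text supports in four ways.

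- **That no baseline is taken.** The plan does not say temperature is recorded only during surgery. It refers to patients being "eligible for the study according to the inclusion and exclusion criteria", but the content of those criteria does not appear. The risk model's inputs are not listed, and the figure after the aim is not shown. Any of these could involve a preoperative temperature. The supportable statement is that none is specified. Even if one exists, no visible text fixes its timing or method, or its use in the analysis.
- **That patients arriving cold are scored as intraoperative events.** This is a natural reading, but with no case definition the documents do not settle it.
- **That the primary comparison is biased.** It is not. Randomisation within risk strata balances patients arriving cold in expectation.
- **That the strongest covariate is lost.** Nothing in the documents ranks covariates. Predicted risk is retained as the stratification factor. The simulation compares baseline adjustment with no adjustment, so it overstates the gain if predicted risk and baseline temperature overlap.

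It can also be argued that separating prevention from rewarming is a preference about the estimand. The trial compares whole warming strategies, and the Specific aim speaks of perioperative hypothermia, which is broader than new cooling during surgery. A patient kept from being hypothermic in surgery meets the primary outcome whatever the arrival temperature. That stands as a defence of the overall comparison. It does not help anyone who wants to know how the effect arises, least of all in the low-risk stratum, where prewarming is the entire intervention.

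**Conclusion.** The point holds as a gap in specification with a cheap remedy. The plan specifies no pre-treatment temperature, and a first intraoperative reading is not a valid baseline in the warm arm. The cost is interpretability and precision, not bias.

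The precision cost is small to moderate:

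- about 2 to 7 power points at 39.9% v 28.4%, starting from about 0.90;
- about 1 point at most at 39.9% v 25.5%;
- about 3 to 13 points only if the effect is as small as 39.9% v 32.4%, where unadjusted power is only about 0.55. The plan does not assume that effect.

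These gains rest on assumed correlations of 0.3 to 0.6, 356 per arm and no adjustment for risk stratum. The share of patients arriving cold, 1% to 8%, rests on assumed temperatures and an assumed 36 °C limit.

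**What to change.** - **Overview of design.** Add one non-invasive temperature reading after consent and before the envelope is opened, hence before any prewarming, by the same method in both arms and all three hospitals. If such a reading is already taken for eligibility or risk scoring, say so and fix its timing and method.
- **Outcome variables.** State how patients already hypothermic at that reading are handled. This needs the hypothermia definition to be written down.
- **Analysis plan.** Analyse the primary outcome with a logistic model containing treatment, the baseline temperature and the risk stratum. Add a sensitivity analysis in patients not hypothermic at baseline. Do not use a post-prewarming reading as a baseline covariate.

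Cost: one reading and one form field per patient, and one more term in the model. The preoperative site may differ from that of the intraoperative probe, so the reading serves as a covariate and not for change scores.

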#### Measurements

Intervention: traditional cotton blanket warm vs. active warm according to risk level

#### Plans for randomization and blinding

Randomization: Patients will be randomized using stratified blocked randomization. The random treatment assignments are placed in sealed, numbered, and opaque envelops who will not be involved in opening them. Two staffs signed and recorded the next unopened envelope before opening the envelope. Investigators will access the allocation about an hour before surgery is expected to start, after consent is obtained. Allocation will thus be remained concealed until the last practical moment.

Blinding: Patients are all blind to the allocation.

Reduce confounding factor: Patients in GA group were given 1.5-2mg/kg Propofol, 0.8mg/kg rocuronium, 2ug/kg fentanyl for induction of anesthesia. After tracheal intubation, anesthesia was continued with sevoflurane in 50% nitrous oxide with oxygen, and end-tidal anesthesia gas is maintained 0.9-1.2 MAC. Supplemental fentanyl doses of 50ug are administered for blood pressure elevation or heart rate increases amounting to more than 10% of baseline.

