#### Sample size estimates

 $\alpha$  (two-sided) = 0.05, power (1- $\beta$ ) = 0.90 A previous study revealed that hypothermia incidence is 39.9%[2]. The control and warming group is 1:1. According to our preresearch Warming effect size = 0.36, 10% drop-out, 793 patients are required in total.

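### In a three-hospital trial only risk level is named as a randomisation stratum, the envelope layout is not stated, and the tests ignore both hospital and risk level: some precision is lost, without bias

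*Combined protocol and SAP*

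**What the plan says.** The Overview of design recruits from an "elective major surgery population in PUMC Hospital, Beijing Hospital and Xuanwu Hospital" and plans a total of about 800. It then says "According to hypothermia risk level, these patients will be stratefied into high, moderate and low risk group", followed by "Patients in each group will be randomly categorize into warm group and control group". Risk level is the only stratum named anywhere in the document.

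Plans for randomization and blinding says "Patients will be randomized using stratified blocked randomization", but lists no factors and gives no block size. On the mechanism it says "The random treatment assignments are placed in sealed, numbered, and opaque envelops" and "Two staffs signed and recorded the next unopened envelope before opening the envelope". It does not say whether envelopes are grouped by hospital, by risk level, or by both.

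The Analysis plan lists Student's t, Wilcoxon rank-sum and chi-square tests between the arms, with no term for hospital or risk level. Sample size estimates adds that "The control and warming group is 1:1" and gives a total of 793.

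**The concern.** With three hospitals and three risk levels, the next envelope has no meaning until the series is specified. Staff at different hospitals could set it up differently.

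The layout that follows most directly from the named stratum is one series per risk level. If the three hospitals share those series, each block fills with patients from several hospitals, and nothing holds the arms level within a hospital. If hospitals differ in incidence of hypothermia, length of stay or cognitive scores, that chance imbalance adds noise to the comparison. The document does not say that the hospitals differ, so this is an assumption. It is plausible mainly for the length-of-stay and cognitive outcomes.

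Separately, the plan stratifies the allocation but not the test, so it gives up precision that the design has already paid for.

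**Working it through.** The plan states no figure for balance, so there is none to reproduce.

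**Inputs from the document:** N = 793 (Sample size estimates), 1:1 allocation, three hospitals, three risk levels, randomisation within risk level.

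**Assumed, because the plan is silent:** equal hospital and risk shares (793/3 = about 264 each); blocks of 4; incidences of 30/40/50% across hospitals and 20/40/60% across risk levels.

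**1. Arm difference within one hospital, risk-level series shared by all hospitals.** Let D be warmed minus control patients in a hospital with share p. Within a balanced block of size b, any two assignments (coded +1 and -1) have correlation -1/(b-1). One block therefore contributes b·p - b·p² to the variance of D, whatever the block size. Over the trial:

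- Var(D) = N·p·(1-p) = 793 × 1/3 × 2/3 = 176, so SD = 13.3.
- Mean |D| = 0.798 × 13.3 = 10.6; 95th percentile = 1.96 × 13.3 = 26.

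Simulation with N = 800 agrees: mean 10 to 11 and 95th percentile 25 to 27 per hospital. With hospital shares of 60/25/15% the means are 8 to 11.

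**2. Largest of the three hospitals, by envelope layout (simulation, N = 793).**

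| Layout | Median | 95th percentile |
|---|---|---|
| One series per risk level, shared and interleaved across hospitals | 15 | about 31 |
| Same series, cut into consecutive runs held by each hospital | 2 to 3 | 5 |
| Nine series, hospital by risk level | 2 | 4 |

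**3. What the worst layout does to the primary comparison.** With incidences of 30/40/50%, the shift in the arm difference is about 0.10 × (D₃ - D₁)/396.5, where 396.5 = 793/2. The three D values sum to about zero, so Cov(D₁, D₃) = -176/2 = -88.

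- Var(D₃ - D₁) = 2 × 176 + 2 × 88 = 528, so SD = 23.
- SD of the shift = 0.10 × 23/396.5 = 0.58 percentage points.
- Median |shift| = 0.674 × 0.58 = 0.4 points; 95th percentile = 1.96 × 0.58 = 1.1 points (simulations give 1.1 to 1.2).
- Standard error of the arm difference = √(4 × 0.4 × 0.6/793) = 3.5 points.

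The shift has expectation zero.

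**4. Share of outcome variance.** Variance of the stratum incidences divided by mean × (1 - mean), with mean 0.4:

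- Hospital: 0.00667/0.24 = 2.8%.
- Risk level: 0.02667/0.24 = 11.1%.

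**5. What the unadjusted test gives up.** Randomising within risk level removes the 11.1% from the true variance of the arm difference, but the unadjusted chi-square still counts it. Its effective critical value is 1.96/√(1 - 0.111) = 2.08, a type I error of about 3.8%. If hospital is balanced as well, it is 1.96/√(1 - 0.139) = 2.11, or about 3.5%. Simulation under assumed risk and hospital spreads gives about 3.6% with 91% power for the unadjusted test, against 4.8% and 93% for a test stratified by hospital and risk level. A check gave power close to these values with 793 × 0.9 = 713 evaluable patients and a true relative reduction of 28.8% (39.9% to 28.4%).

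**The case against.** The strongest case against is that this is missing detail with little consequence. The document never says risk level is the sole stratum, and nothing rules out separate series by hospital. Three hospitals drawing in turn from one physical series would be awkward, and if each holds its own run of envelopes the largest difference falls to about 5 at the 95th percentile. Even with shared series, the efficiency lost by a stratified analysis in the worst hospital is roughly (d/n)²: (15/264)² = 0.3% at the median and (31/264)² = 1.4% at the 95th percentile.

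Most of this stands. It limits the point to precision and makes the shared-series figure a worst case. It does not answer the analysis side: the planned tests use neither factor, whichever envelope layout was intended.

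A reader might go further and infer that risk level itself could be unbalanced, because one mixed-risk series per hospital would produce the same gaps within risk levels. The Overview of design does not support this, since it randomises within each risk group and such a series would contradict it. A reader might also infer that hospital balance is certainly lost. The document is silent on the layout, so that does not follow either.

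**Conclusion.** The point holds as a modest, nearly free improvement in precision. Hospital is not a named stratum, the envelope layout is unstated, and the tests are unadjusted. If risk-level series are shared across hospitals, balance within a hospital is left to chance, with a largest difference of about 15 of 264 patients at the median and about 31 at the 95th percentile. Under a 30/40/50% hospital spread this moves the arm difference by about 1.1 to 1.2 points at the 95th percentile, against a standard error of 3.5. There is no bias, and no imbalance has been shown to exist.

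The larger gain is in the analysis: about 2 points of power and a type I error close to nominal. Most of it comes from using risk level, which carries 11.1% of variance under the assumed spread against 2.8% for hospital. All sizes rest on the assumed shares, block size and incidence spreads. If the hospitals do not differ, the hospital part has no effect on the result.

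**What to change.** In Plans for randomization and blinding, state that randomisation is stratified by hospital and risk level in permuted blocks, that each hospital holds three separately numbered envelope series (one per risk level), and that risk level is entered in the log before the next envelope of that series is opened. Keep the block size out of documents available to recruiting staff.

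In the Analysis plan, compare the arms stratified by hospital and risk level: for example, Cochran-Mantel-Haenszel for hypothermia incidence in place of the unadjusted chi-square, with corresponding stratified or adjusted methods for the other outcomes.

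The cost is nine envelope series to print, a few incomplete blocks at the end of recruitment (95th percentile of the largest difference about 4) and slightly more analysis work. No extra patients are needed. If hospital is already a stratum, one sentence saying so settles the allocation part. If envelopes have already been used, document the layout actually used and make the analysis change, which recovers most of the benefit.

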## Outcome variables

Primary outcome: hypothermia incidence during operation

#### Secondary outcome:

2. The amount of Intraoperative blood loss/blood transfusion

[Time Frame: During operation]

3. Length of stay in PACU

[Time Frame: Postoperative during in postanaesthesia care unit, up to 24 hours after surgery]

4. The incidence of Surgical site infection

[Time Frame: WIthin 30 days postoperative]

5. Lenght of Stay in hospital

[Time Frame: impatient period] up to 6 month after surgery]

6. Lenght of Stay in ICU

[Time Frame: impatient period, up to 6 month after surgery]

7. Incidence of Adverse cardiovascular events

[Time Frame: WIthin 6 month post operation]

8. Incidence of shiver

[Time Frame: during in postanaesthesia care unit. up to 24 hours after surgery]

9. Mini-Mental State Examination (MMSE),

It's a scare to evaluate cognitive function. Total score is 30. Higher values represent a better cognitive function.

[Time Frame: One day preoperation and 1, 7, 30 days postoperation]

10. digit symbol substitution test

The digit symbol substitution test is an evaluation tool used to assess cognitive functioning. It initially was part of the Wechsler Adult Intelligence Test (WAIS), a well-known test that measures an individual's attention. lower digit symbol test scores were correlated with a higher risk of developing dementia in both the five and 10 year groups. Higher values represent a better cognitive function.

[Time Frame: One day preoperation and 1, 7, 30 days postoperation]

11. Auditory Verbal Learning Test,

a memory test that involves learning verbal material, usually single words presented in a list, that is continually presented over repeated trials. Higher values represent a better memory functions.

[Time Frame: One day preoperation and 1, 7, 30 days postoperation]

12. Color Word Stroop Test

The Stroop Colour and Word Test (SCWT) is a neuropsychological test extensively used to assess the ability to inhibit cognitive interference that occurs when the processing of a specific stimulus feature impedes the simultaneous processing of a second stimulus attribute, well-known as the Stroop Effect. Higher values represent a better ability to inhibit cognitive interference.

[Time Frame: One day preoperation and 1, 7, 30 days postoperation]

13. digit span test.

a memory test that involves remember a series of numbers test short time memory Higher values represent a better memory functions.

[Time Frame: One day preoperation and 1, 7, 30 days postoperation]

14. postoperative cognitive dysfunction incidence

- o Z score= (postoperative score-preoperative core) /SD of non-surgical group
- o Two or more than two item in cognitive examination Z score < -1.96
- Z score= (postoperative score-preoperative core) /SD of non-surgical group
  Two or more than two item in cognitive examination Z score < -1.96

[Time Frame: One day preoperation and 1, 7, 30 days postoperation]

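### The POCD Z score is not centred on the non-surgical group's mean change, and its SD is not said to be of change scores, so the absolute POCD incidence cannot be read against the -1.96 cut-off

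*Combined protocol and SAP*

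**What the plan says.** Under the heading for secondary outcomes, the last item is "14. postoperative cognitive dysfunction incidence". Its definition has two parts. The score for each test is "Z score= (postoperative score-preoperative core) /SD of non-surgical group", a formula printed twice in the same form. A patient counts as a case by the rule "Two or more than two item in cognitive examination Z score < -1.96".

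The cognitive tests share one schedule: "Time Frame: One day preoperation and 1, 7, 30 days postoperation". Each of the five tests is described as scored so that a higher value is better; for the MMSE, for example, the text reads "Higher values represent a better cognitive function".

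The Analysis plan lists "Incidence of postoperative cognitive disoerder at7day postoperative" among the outcomes for the chi-square test. It assigns the five scores themselves ("MMSE, AVLT, Digital span, Color Word stroop, digit symbol substitution") to the Wilcoxon rank-sum test. It adds that these tests "will be used to compare the primary and secondary outcomes between groups".

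In the readable text the non-surgical group appears only as the source of the SD. Nothing in the outcome definitions or the Analysis plan subtracts a mean change in that group, mentions practice effects or mentions alternate test forms.

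**The concern.** The value -1.96 is the lower 2.5% point of a normal variable that has been both centred and scaled. The plan scales the change but does not centre it, and it leaves open whether the scaling SD belongs to change scores or to scores at a single visit. The rule therefore flags the lowest 2.5% of non-surgical change on a test only if that group's mean change is zero and the SD is of the change.

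Repeat testing gives a reason to doubt the first condition. The day-7 assessment is the third administration, after the preoperative and day-1 tests. If people improve with repetition, their scores rise and Z moves away from the cut-off. Outcome 14 is named an incidence, and readers will tend to take each arm's figure as an absolute rate. That rate is what is at stake.

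**Working it through.** The documents state no POCD rate, practice effect or reference SD, so there is no figure of the plan's own to reproduce.

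**Step 1: algebra.** For one test, let m be the mean change without surgery, σ the SD of that change, s the SD the plan divides by, and g = m/σ. The plan flags a test when (post - pre)/s < -1.96. In terms of the centred score [(post - pre) - m]/σ, this is the same as being below -1.96 × (s/σ) - g.

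- If s = σ, the effective cut-off is -(1.96 + g).
- If g = 0 but s differs from σ, the cut-off is still not -1.96. A zero mean change is therefore not enough by itself.

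Because higher scores are better, g > 0 moves the cut-off down and cannot add a case. A negative g moves it up.

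**Step 2: one test, no decline, s = σ.** The flagged fraction is Φ(-1.96 - g): 2.50% at g = 0, 1.19% at g = 0.3 and 0.69% at g = 0.5.

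**Step 3: incidence.** The following inputs are assumptions, not taken from the documents: the gain g, the decline D in SD units, the inter-test correlation, and s = σ. The battery of five tests is inferred from the outcome list and the Analysis plan.

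- Independent tests: p = Φ(-1.96 + D - g), and incidence is the binomial probability of at least 2 of 5.
- Correlation 0.3: the same binomial with p(F) = Φ((-1.96 + D - g - √0.3 F)/√0.7), integrated over F ~ N(0,1).
- Subset model: a fraction f declines by D and the rest do not, so incidence = f × P(D) + (1 - f) × P(0).

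For example, with D = 1 and independent tests, p = Φ(-0.96) = 16.85% at g = 0, which gives 20.0%. At g = 0.5, p = Φ(-1.46) = 7.21%, which gives 4.5%.

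| POCD incidence, % | g = 0 | 0.1 | 0.3 | 0.5 |
|---|---|---|---|---|
| All decline 1 SD, independent | 20.0 | 15.5 | 8.7 | 4.5 |
| All decline 1 SD, correlation 0.3 | 22.3 | 18.4 | 12.0 | 7.4 |
| Same, gain on three tests only, correlation 0.3 | 22.3 | 20.0 | 16.0 | 12.8 |
| 20% decline 3 SD, correlation 0.3 | 20.9 | 20.4 | 19.4 | 18.4 |
| 12% decline 3 SD, correlation 0.3 | 13.2 | 12.7 | 11.9 | 11.1 |

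The g = 0 column is the result of the centred rule. With a reference change of -0.1 SD, the 1 SD rows rise to 25.2% (independent) and 26.7% (correlation 0.3).

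**Step 4: between-arm comparison.** The same formula applies to both arms, so if the arms do not differ in cognition their expected POCD rates are equal and the chi-square test keeps its type I error. Power was computed for a two-sided 0.05 test of two proportions with 793 × 0.9 / 2 = 356 per arm (rounded down) and correlation 0.3. The arm contrasts are assumed.

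| Arm contrast | Power at g = 0, % | Power at g = 0.5, % |
|---|---|---|
| All decline, 1 v 0.75 SD | 87.3 | 58.0 |
| 20% v 12% decline 2 SD | 62.2 | 46.6 |
| 20% v 12% decline 3 SD | 78.1 | 78.0 |
| 20% v 12% decline 4 SD | 79.2 | 82.3 |
| All decline, 2.5 v 2.25 SD | 82.3 | 94.7 |

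Power can fall, stay level or rise. The Wilcoxon tests are listed for the scores themselves and do not use Z, and intraoperative hypothermia does not involve these tests.

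**The case against.** The strongest reply is that the harm lies outside the planned inference. The Analysis plan uses POCD only to compare arms, and that comparison remains valid. No external benchmark or decision rests on the absolute rate. This stands, and it limits the point to how the arm-level rates are read.

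The harm is also conditional. The documents report no practice effect. A reader might infer that the POCD rate is understated; the documents do not support that. At zero mean change, with an SD of change, nothing is lost, and a negative reference change would raise the rate. Even with a positive gain, integer scores or a ceiling (the MMSE maximum is 30) may mean that no patient is reclassified.

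A reader might also infer that the rate would be too low against the truth. That does not follow either; the shift is relative to the centred -1.96 rule. In the 3 SD subset model, with 20% of patients truly affected, the centred rule gives 20.9%, while the plan's formula gives 20.4% and 19.4% at gains of 0.1 and 0.3, both closer to 20%. With 12% affected, the plan's formula is closer at 0.1, 0.3 and 0.5.

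Finally, the large drop to 7.4% depends on a uniform decline chosen for illustration, and all the computed rates assume that the SD is of the change. Both remarks are fair. The second strengthens the point, because the definition leaves the denominator open as well. The absence of a described non-surgical group should not be pressed, since part of the document was removed before review and a figure is not shown.

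**Conclusion.** The definition is incomplete in a way that matters for one secondary outcome. It applies -1.96 to an uncentred score whose SD is not specified as that of change. With an SD of change, a positive mean gain of g SD makes the effective centred cut-off -(1.96 + g), so POCD incidence in both arms falls or stays the same relative to the centred rule.

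The size cannot be determined from the documents. Over assumed gains up to 0.5 SD with correlation 0.3, the fall ranges from 2.5 percentage points (20.9% - 18.4%) to 14.9 points (22.3% - 7.4%), depending on how decline is spread among patients.

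Two stronger readings should be resisted. The formula does not bias the between-arm chi-square test under the null, and it does not necessarily cost power. The primary outcome and the Wilcoxon comparisons of the five scores are untouched. The correction should be made because the plan labels this outcome an incidence, but it does not threaten the trial's main result.

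**What to change.** Define, for each test, Z = [(post - pre) - mean change in the non-surgical group] / SD of the change in that group, with both reference quantities taken over the same interval as the trial assessment (day 7 for the planned test). Name the reference data set and fix it before any between-arm comparison. State which tests count towards the two-or-more rule.

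This rewords one formula and adds no procedures for trial patients. The cost is that the non-surgical data must supply a mean and SD of change for every test at that interval. If the existing SD is already of change over that interval, the same data yield the mean. If the data cannot supply both, label the arm-level POCD rates as not practice-corrected and interpret only the between-arm comparison. The change should not be presented as a gain in power.
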